1. *Effect on platelet function - risk for bleeding:* BTK is a signaling molecule in one of several platelet activation pathways, and clinically relevant effects of remibrutinib on platelet functions were observed in the remibrutinib preclinical toxicology program. The mode of

action by which remibrutinib could potentially cause bleeding is currently not fully understood. In vitro assessments suggest a target-related impact on platelets, similar to effects induced by the BTK inhibitor ibrutinib, which has been shown to inhibit clot retraction ([Bye et al 2015](#)). Furthermore, remibrutinib inhibited collagen-induced platelet aggregation. BTK inhibition does not have any impact on the plasmatic coagulation system and, plasmatic coagulation was not affected in the human Phase 1 study up to the highest dose of 600 mg remibrutinib. In CSU, in the completed core CLOU064A2201 Phase 2b study, 18 (6.7%) non-serious bleeding events were reported in any remibrutinib arm compared to one event on placebo (2.4%); none of the AEs was serious or severe. All the bleeding AEs events reported were mild, except 2 moderate AEs: gingival bleeding and hematuria. Two bleeding events (petechiae and hematuria) led to study treatment discontinuation. There were no notable clinically relevant abnormalities for coagulation parameters, hemoglobin levels and platelet counts noted in these studies. In the interim analysis of the open-label long-term (up to 52 weeks) extension trial CLOU064A2201E1, the rate of bleeding events (4.4%) was comparable to that seen in the core trial; all events were non-serious, all but 2 events (the purpura and heavy menstrual bleeding in the setting of leiomyoma) were mild in severity. Potential effects of remibrutinib on hemostasis should be monitored both clinically and by standard, validated laboratory measures including complete blood count and standard coagulation parameters. Clinical monitoring should focus on skin (bruising, petechiae) and mucosa (e.g., gastro-intestinal (GI) tract bleeding including gingival, rectal, and conjunctival bleeding). i.e., Patients with a known history of bleeding disorders, or with a history of clinically relevant gastrointestinal bleeding and patients requiring anti-platelet or anticoagulant therapy (other than aspirin up to 100 mg/d or clopidogrel up to 75 mg/d) are excluded from the trial; the use of dual anti-platelet therapy (e.g., acetylsalicylic acid + clopidogrel) is prohibited (see details in [Section 5.2](#) and [Section 6.2.3](#)). In case of a significant bleeding event, study treatment must be discontinued immediately. Please, refer to the current IB for further details.

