6.6 Dose escalation and dose modification

Investigational or other study treatment dose adjustments are not permitted.

Study treatment interruptions are permitted in order to manage the following events:

- Management of bleeding events: in case of planned surgery with clinical significant bleeding risk, interruption of study treatment 7 days before the surgery is required; after recovery, participant may re-start study treatment after 7 days.
- Management of participants in case of Hepatitis B re-activation (new appearance of detectable HBV-DNA or positive HBsAg): participants should start antiviral treatment according to local clinical practice and interrupt study treatment until HBV-DNA and HBsAg reach an undetectable level, and then re-start study treatment.

Study treatment interruption for other than the above reasons is only permitted if, in the opinion of the investigator, a participant is deemed to be at a significant safety risk unless administration of investigational treatment is temporarily interrupted. In such cases study treatment should be interrupted only during the time that this risk is present and ongoing. Study treatment can be re-started at the next scheduled visit after resolution of the safety risk.

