9.1.1 Discontinuation from study treatment

Discontinuation of study treatment for a participant occurs when study treatment is permanently stopped for any reason (prior to the protocol planned completion of study drug administration) and can be initiated by either the participant or the investigator.

The investigator must discontinue study treatment for a given participant if, he/she believes that continuation would negatively impact the participant's well-being.

Discontinuation from study treatment is required under the following circumstances:

- Participant decision (requested in writing or verbally)

- Pregnancy
- Use of prohibited treatment requiring study treatment discontinuation as detailed in [Table 6-3](#) or discontinuation of highly effective methods of contraception as detailed in [Section 5.2](#)
- Any situation in which continued study participation might result in a safety risk to the participant
- Following emergency unblinding
- Emergence of the following AEs:
 - any adverse events that in the judgement of investigator, taking into consideration the participant's overall status, prevents the participant from continuing participation in the study, including:
 - hypersensitivity reactions,
 - severe/serious infections,
 - clinically significant spontaneous bleeding events
 - new confirmed diagnosis of malignancy of any organ system
(other than localized basal cell carcinoma of the skin or in situ cervical cancer)
 - Platelets < 75 000/mm³
 - Abnormal renal laboratory results requiring discontinuation (see [Section 16.3](#))
 - Abnormal liver laboratory results requiring discontinuation (see [Section 16.2](#))
 - Any other laboratory abnormalities that in the judgment of the investigator, taking into consideration the participant's overall status, prevents the participant from continuing participation in the study
 - participant received a live virus vaccination during the study

[figure not shown]
If discontinuation from study treatment occurs, the investigator should make a reasonable effort to understand the primary reason for the participant's discontinuation from study treatment and record this information.

All participants who discontinue from study treatment prematurely should complete the Early treatment discontinuation visit at the time of treatment discontinuation.

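### Section 4.5 makes a significant bleed a mandatory permanent stop, but the required-discontinuation list in Section 9.1.1 names only spontaneous bleeds, under investigator judgement

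*Protocol*

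**What the plan says.** Protocol Section 4.5, in the paragraph on platelet function and bleeding, gives the rule: "In case of a significant bleeding event, study treatment must be discontinued immediately". The same sentence stands in Table 6-3 (Section 6.2.3), in the action cells for prohibited anticoagulant and anti-platelet medication.

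Section 9.1.1 defines the term: "Discontinuation of study treatment for a participant occurs when study treatment is permanently stopped for any reason". The glossary agrees. Section 9.1.1 then opens its list with "Discontinuation from study treatment is required under the following circumstances". Bleeding appears there once, as "clinically significant spontaneous bleeding events". That entry is one of the examples following "any adverse events that in the judgement of investigator, taking into consideration the participant's overall status", where the test is whether the event prevents continued participation.

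Two other provisions of Section 9.1.1 are broader. One list item is "Any situation in which continued study participation might result in a safety risk to the participant". Ahead of the list stands a general duty: "The investigator must discontinue study treatment for a given participant if, he/she believes that continuation would negatively impact" the participant's well-being.

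Section 6.6 deals with interruption. Its item on managing bleeding events covers planned surgery only. For reasons other than those it lists, interruption is "only permitted if, in the opinion of the investigator, a participant is deemed to be at a significant safety risk" without a temporary pause, and treatment may resume at the next scheduled visit once the risk has resolved.

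**The concern.** Bleeding is a named potential risk of the drug. Section 4.5 reports platelet effects in the preclinical programme, inhibition of collagen-induced platelet aggregation, and a mechanism that is not fully understood. In Phase 2b it reports bleeding in 6.7% on any remibrutinib dose against 2.4% on placebo. A drug effect on platelets matters for a bleed provoked by injury or a procedure as well as for a spontaneous one, and the Section 4.5 rule covers both.

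Section 9.1.1 is where the protocol collects the events that require treatment to stop. An investigator who consults it after a traumatic or procedural bleed finds a bleeding entry that does not match the event, under a clause that leaves the decision to judgement. The same bleed could end treatment at one site and lead to a pause and restart at another. What is at stake is participant safety and consistent conduct. Inconsistent handling would also carry into the SAP Section 2.7.1.1 summaries of action taken and interruption duration for bleeding events.

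**Working it through.** No arithmetic applies. The check sets the provisions side by side and then runs one case through them.

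**Comparison of the rules**

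| Provision | Trigger | Limited by cause? | Judgement on stopping? | Consequence |
|---|---|---|---|---|
| Section 4.5 | Significant bleed | No | No | Immediate discontinuation |
| Table 6-3, two rows | Significant bleed in a participant on prohibited anticoagulant or anti-platelet drugs | No | No | Immediate discontinuation |
| Section 9.1.1, bleeding entry | Clinically significant bleed | Yes, spontaneous only | Yes | Discontinuation |
| Section 9.1.1, safety-risk item and well-being duty | General safety or well-being | No | Depends on assessing the individual situation | Discontinuation |
| Section 6.6, general clause | Significant safety risk | No | Yes | Interruption, then restart |

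**Does discontinued mean a permanent stop?** Yes. The glossary and Section 9.1.1 both say so. Table 6-3 also keeps the terms apart within single cells: study medication is interrupted until the anticoagulant or anti-platelet effect has ended, but discontinued for a significant bleed. Discontinued cannot fairly be read as paused.

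**A test case.** A participant on no anticoagulant or anti-platelet drug has a significant bleed after an injury, and the investigator considers it resolved.

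1. Section 4.5: treatment ends permanently.
2. Table 6-3: not relevant, because its sentence sits in the prohibited-drug rows.
3. Section 9.1.1, bleeding entry: not met, because the bleed was not spontaneous.
4. Section 9.1.1, general provisions: these apply only if continuing is assessed as a risk or as harmful. An investigator who regards the bleed as resolved may conclude otherwise.
5. Section 6.6: a site that has not carried Section 4.5 into its reading could treat the event as an interruption and restart.

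For a participant on neither drug class, the full rule appears only in Section 4.5. Section 9.1.1 does not repeat it or refer to it for bleeding. The list can hold items that need no judgement, pregnancy being one, so its format does not force the weaker wording.

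**Frequency.** The documents do not define a significant bleeding event, do not give the share of bleeds that are provoked, and describe none of the bleeds named in Section 4.5 as traumatic or procedural. Exclusion criterion 12 bars planned surgery, so planned procedural bleeds should be uncommon. No rate follows from this.

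**The case against.** The strongest reply is that nothing is missing. Section 4.5 is protocol text, and Section 13.2 has the investigator agree to follow all of the protocol's instructions, so a restart after a significant bleed would be a breach whatever Section 9.1.1 says. The examples in Section 9.1.1 are introduced as inclusions and are not a closed list, and its safety-risk item and well-being duty can reach a provoked bleed. This stands, and it is why the point is limited. A reader might infer that the protocol gives opposite instructions or tells sites to restart; it does neither. What remains is that the general provisions work through assessment of the individual case, whereas Section 4.5 makes the stop automatic, and the protocol states no order of precedence.

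A reader might also treat Section 6.6 as a separate defect because its restart clause does not exclude bleeds. That goes too far. The clause does not exclude pregnancy or new malignancy either, and a general permission to interrupt does not override a specific duty to stop.

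Nor does Table 6-3 supply further general statements of the rule, since its two sentences apply only to the prohibited drugs in their rows.

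The restriction to spontaneous bleeds may have been deliberate; the documents do not settle this. If it was, Section 4.5 and Table 6-3 are too broad, and an edit is still needed. Section 4.5 also refers to the Investigator's Brochure for further details, which may include a definition or management guidance not available here.

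**Conclusion.** The point holds as a limited inconsistency in a safety stopping rule. Section 4.5 requires a permanent stop for any significant bleed. Section 9.1.1 carries this over only for spontaneous bleeds and only under investigator judgement. The conclusion rests on the protocol's own definition of discontinuation and on reading the bleeding entry as an example under the judgement clause, as its wording indicates.

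The size cannot be estimated. A reader might infer a ceiling from the absence of serious bleeds in Phase 2b and in the extension interim analysis. The documents do not support one. It would equate significant with serious, yet two non-serious Phase 2b bleeds (petechiae and hematuria) led to treatment discontinuation. It would also carry data from up to 12 weeks, or a median of 35.14 weeks, over to treatment of up to 52 weeks.

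The primary analysis is essentially unaffected, because the primary estimand handles treatment discontinuation for any reason by a treatment policy strategy.

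**What to change.** In Section 9.1.1, list *any clinically significant bleeding event* as a required discontinuation item of its own, outside the judgement clause, delete the word spontaneous, and cross-refer to Section 4.5. Judgement then remains on whether a bleed is significant, but not on whether a significant bleed ends treatment. If the sponsor confirms that only spontaneous bleeds were meant, align Section 4.5 and Table 6-3 to that instead. One line in Section 6.6, saying that restart does not apply after an event requiring discontinuation under Section 9.1.1, would help but is optional.

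The cost is wording in an amendment or clarification letter, with no added visits or procedures. The downside of the main option is that a few participants with a provoked significant bleed stop permanently instead of restarting, which Section 4.5 already requires.

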4.6 Rationale for Public Health Emergency mitigation procedures

During a Public Health emergency as declared by Local or Regional authorities, i.e., pandemic, epidemic or natural disaster, mitigation procedures to ensure participant safety and trial integrity are listed in relevant sections. Notification of the Public health emergency should be discussed with Novartis prior to implementation of mitigation procedures, and permitted/approved by Local or Regional Health Authorities and Ethics Committees as appropriate.

5 Study Population

The study population will consist of approximately 450 randomized female and male adult participants (300 in the active arm and 150 in the placebo arm) with CSU inadequately controlled by second generation H1-antihistamines (at least at locally label approved dose).

The screen failure rate is estimated to be 30%, meaning approximately 645 participants are expected to be screened.

Participants will be stratified based on prior exposure to anti-IgE biologics and geographic region; maximum number of participants with prior exposure to anti-IgE biologics will be limited to approximately 30% of the total study population.

Participants who drop out after they have been randomized will not be replaced.

5.1 Inclusion criteria

Participants eligible for inclusion in this study must meet **all** of the following criteria:

1. Signed informed consent must be obtained prior to participation in the study
2. Male and female adult participants ≥ 18 years of age at the time of screening
3. CSU duration for ≥ 6 months prior to screening (defined as the onset of CSU determined by the investigator based on all available supporting documentation)

4. Diagnosis of CSU inadequately controlled by second generation H1-antihistamines at the time of randomization defined as:
 - The presence of itch and hives for ≥ 6 consecutive weeks prior to screening despite the use of second generation H1-antihistamines during this time period
 - UAS7 score (range 0-42) ≥ 16 , ISS7 score (range 0-21) ≥ 6 and HSS7 score (range 0-21) ≥ 6 during the 7 days prior to randomization (Day 1)
5. Documentation of hives within three months before randomization (either at screening and/or at randomization; or documented in the participants' medical history)
6. Willing and able to complete an Urticaria Patient Daily Diary (UPDD) for the duration of the study and adhere to the study protocol
7. Participants must not have had more than one missing UPDD entry (either morning or evening) in the 7 days prior to randomization (Day 1)

5.2 Exclusion criteria

Participants meeting any of the following criteria are not eligible for inclusion in this study.

Evaluation of participant eligibility for laboratory parameters listed below must be based on central laboratory results. In case eligibility criteria are not met for specific laboratory parameters, these may be re-tested a maximum of once during the screening period.

No additional exclusions may be applied by the investigator, in order to ensure that the study population will be representative of all eligible participants.

1. Use of other investigational drugs within 5 half-lives, or within 30 days (for small molecules) prior to Screening or until the expected pharmacodynamic (PD) effect has returned to baseline (for biologics), whichever is longer; or longer if required by local regulations
2. Previous use of remibrutinib or other BTK inhibitors
3. History of hypersensitivity to any of the study treatments or its excipients or to drugs of similar chemical classes
4. Participants having a clearly defined predominant or sole trigger of their chronic urticaria (chronic inducible urticaria) including urticaria factitia (symptomatic dermatographism), cold-, heat-, solar-, pressure-, delayed pressure-, aquagenic-, cholinergic-, or contact-urticaria
5. Other diseases with symptoms of urticaria or angioedema, including but not limited to urticaria vasculitis, urticaria pigmentosa, erythema multiforme, mastocytosis, hereditary urticaria, or drug-induced urticaria
6. Any other skin disease associated with chronic itching that might influence in the investigator's opinion the study evaluations and results, e.g., atopic dermatitis, bullous pemphigoid, dermatitis herpetiformis, senile pruritus or psoriasis
7. Participants taking medications prohibited by the protocol (see [Table 6-3](#))
8. Known history or evidence of ongoing alcohol or drug abuse within the last 6 months before randomization

9. History of malignancy of any organ system (other than localized basal cell carcinoma of the skin or in situ cervical cancer), treated or untreated, within the past 5 years, regardless of whether there is evidence of local recurrence or metastases
10. Pregnant or nursing (lactating) women
11. Women of child-bearing potential (WoCBP), defined as all women physiologically capable of becoming pregnant, unless they are using highly effective methods of contraception during dosing and for 7 days after stopping of study treatment. Highly effective contraception methods include:
 - Total abstinence (when this is in line with the preferred and usual lifestyle of the participant). Periodic abstinence (e.g., calendar, ovulation, symptothermal, post-ovulation methods) and withdrawal are not acceptable methods of contraception
 - Female sterilization (have had surgical bilateral oophorectomy with or without hysterectomy) total hysterectomy or bilateral tubal ligation at least six weeks before taking investigational drug. In case of oophorectomy alone, only when the reproductive status of the woman has been confirmed by follow up hormone level assessment
 - Male sterilization (at least 6 months prior to screening). For female participants on the study, the vasectomized male partner should be the sole partner for that participant
 - Use of oral, (estrogen and progesterone), injected or implanted hormonal methods of contraception

In case of use of oral contraception women should have been stable on the same pill for a minimum of 3 months before taking investigational drug.

Women are considered post-menopausal if they have had 12 months of natural (spontaneous) amenorrhea with an appropriate clinical profile (e.g., age appropriate, history of vasomotor symptoms). Women are considered not of child bearing potential if they are post-menopausal or have had surgical bilateral oophorectomy (with or without hysterectomy), total hysterectomy or bilateral tubal ligation at least six weeks ago. In the case of oophorectomy alone, only when the reproductive status of the woman has been confirmed by follow-up hormone level assessment is she considered not of child bearing potential.

If local regulations deviate from the contraception methods listed above to prevent pregnancy, local regulations apply and will be described in the informed consent form (ICF).

[figure not shown]
12. Major surgery within 8 weeks prior to screening or planned surgery for the duration of the study
- 13.a History of live attenuated vaccine within 6 weeks prior to randomization or requirement to receive these vaccinations at any time during the study
14. Evidence of clinically significant cardiovascular (such as but not limited to myocardial infarction, unstable ischemic heart disease, NYHA Class III/IV left ventricular failure, arrhythmia and uncontrolled hypertension within 12 months prior to Visit 1), neurological, psychiatric, pulmonary, renal, hepatic, endocrine, metabolic, hematological disorders, gastrointestinal disease or immunodeficiency that, in the investigator's opinion, would

- compromise the safety of the participant, interfere with the interpretation of the study results or otherwise preclude participation or protocol adherence of the participant
15. Uncontrolled disease states, such as asthma, or inflammatory bowel disease, where flares are commonly treated with oral or parenteral corticosteroids
 16. Hematology parameters at screening:
 - Hemoglobin: < 10 g/dl
 - Platelets: < 100 000/mm³
 - Leucocytes: < 3 000/mm³
 - Neutrophils: < 1 500/mm³
 17. Significant bleeding risk or coagulation disorders
 - 18.a History of gastrointestinal bleeding, e.g., in association with use of nonsteroidal anti-inflammatory drugs (NSAID), that was clinically relevant (e.g., where intervention was indicated or requiring hospitalization or blood transfusion)
 - 19.a Requirement for anti-platelet medication, except for acetylsalicylic acid up to 100 mg/d or clopidogrel up to 75 mg/d. The use of dual anti-platelet therapy (e.g., acetylsalicylic acid + clopidogrel) is prohibited.
 20. Requirement for anticoagulant medication (for example, warfarin or Novel Oral Anti-Coagulants (NOAC))
 21. History or current hepatic disease including but not limited to acute or chronic hepatitis, cirrhosis or hepatic failure or Aspartate Aminotransferase (AST)/ Alanine Aminotransferase (ALT) levels of more than 1.5 x upper limit of normal (ULN) or International Normalized Ratio (INR) of more than 1.5 at screening
 22. History of renal disease, creatinine level above 1.5x ULN, or estimated Glomerular Filtration Rate (eGFR) < 45ml/min (using the Cockcroft-Gault equation) at screening
 23. Evidence of an ongoing Hepatitis C infection (e.g., defined by the detection of hepatitis C virus ribonucleic acid (HCV-RNA) at screening) and/or an ongoing Hepatitis B infection (defined by the detection of hepatitis B virus surface antigen (HBsAg) and/or hepatitis B virus (HBV)-DNA at screening; participants who are positive for anti-hepatitis B core (HBc) antibodies but who are negative for antibodies against HBsAg and HBV-DNA can be included into the study if they agree to monitoring for HBsAg and HBV-DNA re-activation)
 24. Known or suspected ongoing, chronic or recurrent infectious disease including but not limited to opportunistic infections (e.g., tuberculosis, atypical mycobacterioses, listeriosis or aspergillosis) and/or known positivity for Human Immunodeficiency Virus (HIV) infection. HIV antigen/antibody tests will be performed to determine HIV status if required according to local regulations.

6 Treatment

[figure not shown]
